#### **I8B-MC-ITSD Statistical Analysis Plan Version 2**

Endpoint	Analysis Period	Statistical Method
Incidence of hypoglycemic events All Documented a Nocturnal a Documented Symptomatic a Non-Nocturnal (or Daytime) (Documented and between waking and bedtime) a	0-12, 0-26, 12-26 weeks	Logistic regression with treatment as an independent variable.
Rate of postmeal hypoglycemic events (per patient per 30 days / year) for all 3 main meals Documented Symptomatic a	$\leq 0.5, \leq 1, \leq 2, \leq 4, >1$ to $\leq 2, >2$ to $\leq 4$ and >4 hours after start of a meal within 0-12, 12-26, 0-26 weeks	Negative binomial regression with treatment, and log (exposure/30 days or exposure/365.25 days) as the offset in the model.
Incidence of postmeal hypoglycemic events for all 3 main meals Documented Symptomatic a	$\leq 0.5, \leq 1, \leq 2, \leq 4, >1$ to $\leq 2, >2$ to $\leq 4$ and >4 hours after start of a meal within 0-12,12-26, 0-26 weeks	Logistic regression with treatment as an independent variable.
Rate of severe hypoglycemic events (per patient per year / 100 years)	0-12, 0-26, 12-26 weeks	Exposure adjusted rate per year / 100 years (calculated by total number of events divided by total exposure for individual patients) will be provided and the empirical method (see 0 for details) will be used for treatment comparison.

Endpoint	Analysis Period	Statistical Method
Incidence of severe hypoglycemic	0-12, 0-26, 12-26 weeks	Proportion of patients with severe
events		hypoglycemia will be reported. The
		treatment comparison will be based on
		a logistic regression model with
		treatment as an independent variable.
Rate of postmeal severe	$\leq 0.5, \leq 1, \leq 2, \leq 4, >1$ to $\leq 2, >2$	Due to limit data for the rare event,
hypoglycemic events (per patient per	to $\leq$ 4 and $>$ 4 hours after start of	only summary statistics will be
year / 100 years) for all 3 main meals	a meal within 0-12,12-26, 0-26	provided by treatment. No statistical
	weeks	comparison will be conducted.
Incidence of postmeal severe	$\leq 0.5, \leq 1, \leq 2, \leq 4, >1$ to $\leq 2, >2$	Fisher exact test will be used for
hypoglycemic events for all 3 main	to $\leq$ 4 and $>$ 4 hours after start of	treatment comparison.
meals	a meal within 0-12, 12-26, 0-	
	26weeks	

Summary of Analyses for Endpoints Related to Hypoglycemia

a All documented hypoglycemia and the subcategories based on the thresholds of blood glucose ≤70 mg/dL and blood glucose <54 mg/dL will be analyzed, all postmeal hypoglycemia based on the threshold of ≤70 mg/dL and <54 mg/dL will be applied.

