Hypoglycemia rates will be summarized for periods of 30 days, 1 year, and 100 years (severe hypoglycemia only). The rate of severe hypoglycemia per 100 years will be compared between treatment groups using the empirical method (details will be described in the SAP). For each of the other categories of hypoglycemia, the number of hypoglycemia events during a specific period (rate) after randomization (for example, Weeks 0-12 of treatment period) will be analyzed by using a negative binomial regression model. The model will include treatment and the baseline hypoglycemia rate (measured during lead-in) as a covariate. An offset defined as the log transformation of treatment exposure in the specific period (days)/365.25 days (or 30 days) will be included in the model to estimate the rate of hypoglycemia per year (or per 30 days). The proportion of patients with at least 1 hypoglycemic event in each category (incidence) during a specific period after randomization will be analyzed using a logistic regression model including treatment and baseline hypoglycemia rate value in the model.

Continuous safety variables, as well as the change from baseline for these variables, will be analyzed by MMRM or ANCOVA models. For categorical variables, Fisher's exact test will be used to compare treatment groups unless otherwise specified. The analyses for assessing immunogenicity data will be described in the SAP.

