The incidence and number of episodes of hypoglycemia (regardless of the type of hypoglycemia event) during the MMTT will be summarized by treatment and time relative to the meal ( $\leq 0.5$ ,  $\leq 1$ ,  $\leq 2$ ,  $\leq 4$ , >1 to  $\leq 2$  and >2 to  $\leq 4$  hours after start of the meal) and analyzed by Fisher's exact test.

A listing of patients with at least 1 severe hypoglycemia reported (as SAE) after randomization will be provided. Summary of severe hypoglycemia treatment and outcome from the patient diary will be provided.

A list of MedDRA PTs will be used for the narrow search of potential severe hypoglycemia in spontaneously reported AEs. The events identified through the search strategy that are also reported as SAEs will be summarized and compared between treatments. Fisher's exact test will be used to assess the treatment difference in the proportion of patients with potential severe hypoglycemia.

Analysis Period	Statistical Method
0-12, 0-26, 12-26weeks	Negative binomial regression with
	treatment, and log (exposure/30
	days for exposure/365.25 days) as
	the offset in the model.

 Table 6.5.
 Summary of Analyses for Endpoints Related to Hypoglycemia

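### Severe-hypoglycemia incidence is compared by a treatment-only logistic model with no test type and no rule for an arm without events

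*SAP*

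**What the plan says.** SAP section 6.12.4.1 refers to Table 6.5 for the methods of every hypoglycemia endpoint. The row for incidence of severe events covers "0-12, 0-26, 12-26 weeks". It first reports the "Proportion of patients with severe" hypoglycemia; the "treatment comparison will be based on" "a logistic regression model with" treatment as the explanatory variable. The row stops there: it does not mention Wald, likelihood-ratio or score tests, a penalized or exact version, or sparse data.

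Elsewhere the plan treats similar endpoints differently:

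- Postmeal severe event rate (next row of Table 6.5): no comparison at all, "Due to limit data for the rare event".
- Postmeal severe incidence (the row after that): "Fisher exact test will be used for" the comparison.
- Potential severe hypoglycemia found by a preferred-term search and also reported as serious (section 6.12.4.1): "Fisher's exact test will be used to assess the treatment difference in the proportion of patients with potential severe hypoglycemia".
- Categorical measures in general (section 6.1): Fisher's exact test.

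Protocol section 10.3.4 also specifies logistic regression for hypoglycemia incidence: it "will be analyzed using a logistic regression model including treatment and baseline hypoglycemia rate value in the model". It has no rare-event provision either. SAP version 2 removed the baseline rate from the hypoglycemia models, which leaves treatment alone.

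**The concern.** Severe hypoglycemia is a main safety question for a mealtime insulin, and the plan itself treats its postmeal form as rare. Protocol section 6.2 also excludes patients with hypoglycemia unawareness or more than one severe episode in the previous six months, which should lower the incidence further. With about 175 patients per arm and windows as short as 12 weeks, an arm with no events is plausible.

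A logistic model fitted by maximum likelihood then has no finite treatment effect. The planned odds ratio and confidence interval cannot be reported, and the p-value depends on which test the software prints. The analyst would have to choose a replacement after seeing the zero, when the candidate tests disagree.

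**Working it through.** **Inputs.** The plan gives no expected frequency or power for severe hypoglycemia, so there is no stated figure to reproduce on this endpoint. The only sizing is for HbA1c: 298 / (1 - 0.15) = 350.6, stated as about 350. With 1:1 allocation that is 175 per arm, used here for every window on the assumption that all randomized patients are dosed. The incidences below are assumptions.

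**Step 1: the estimate.** With 0 of 175 in one arm, the fitted log odds there is ln(0/175), which is minus infinity, so the log odds ratio has no finite maximum. The printed value only reflects when iteration stops. For 0 vs 4:

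| Iterations | Log odds ratio | SE | Wald p |
|---|---|---|---|
| 8 | -5.8 | 5.5 | 0.29 |
| 15 | -12.8 | 181 | 0.94 |
| 25 | -22.8 | 26,920 | 0.999 |

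**Step 2: the p-value.** For 0 vs e events:

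- Let l(k; n) = k ln(k/n) + (n - k) ln(1 - k/n). The likelihood-ratio statistic is 2[l(0; 175) + l(e; 175) - l(e; 350)].
 - e = 4: 2(0 - 19.068 + 21.864) = 5.59, p = 0.018.
 - e = 6: 2(0 - 26.134 + 30.345) = 8.42, p = 0.004.
- The score statistic is 350e / (350 - e).
 - e = 4: 1400/346 = 4.05, p = 0.044.
 - e = 6: 2100/344 = 6.10, p = 0.013.

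| Split of 175 vs 175 | Wald (8 to 25 iterations) | Likelihood ratio | Score | Fisher | Firth OR (penalized LR p) |
|---|---|---|---|---|---|
| 0 vs 3 | 0.32 to 0.999 | 0.041 | 0.082 | 0.248 | 0.14 (0.110) |
| 0 vs 4 | 0.29 to 0.999 | 0.018 | 0.044 | 0.123 | 0.11 (0.054) |
| 0 vs 5 | 0.27 to 0.999 | 0.008 | 0.024 | 0.061 | 0.09 (0.026) |
| 0 vs 6 | 0.26 to 0.999 | 0.004 | 0.013 | 0.030 | 0.07 (0.013) |

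The tests of this one model fall on both sides of 0.05, and the likelihood-ratio p-value is far below Fisher's.

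**Step 3: how often an arm is empty.** With equal true incidence p, let q = (1 - p)^175. Exactly one arm is empty with probability 2q(1 - q), both with q². The shorter windows are taken to carry half the 26-week risk.

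| 26-week incidence | q | One arm empty, 0-26 | Both empty, 0-26 | One empty, half risk | Both empty, half risk |
|---|---|---|---|---|---|
| 0.5% | 0.416 | 48.6% | 17.3% | 45.8% | 41.6% |
| 1% | 0.172 | 28.5% | 3.0% | 48.6% | 17.3% |
| 2% | 0.029 | 5.7% | 0.1% | 28.5% | 3.0% |
| 3% | 0.005 | 1.0% | about 0 | 13.2% | 0.5% |

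From about 1% upwards, one empty arm is more likely in the shorter windows. At 0.5% it is slightly less likely, because both arms are then often empty.

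**Step 4: how often significance would change.** Fisher reaches 0.05 against an empty arm only from 0 vs 6 upwards, so a Wald result would miss a Fisher-significant difference only there.

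- Equal risk, 2q × P(X ≥ 6): 0.02%, 0.3% and 0.8% at 0.5%, 1% and 2%.
- Unequal risk, q of the lower-risk arm × P(X ≥ 6) in the other:
 - 0.5% vs 2%: 0.416 × 0.140 = 5.8%.
 - 0.5% vs 3%: 0.416 × 0.428 = 17.8%.
 - 1% vs 3%: 0.172 × 0.428 = 7.4%.

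**The case against.** The strongest reply is that the plan as a whole would not miss an imbalance. Severe episodes must be reported as serious adverse events. SAP section 6.12.4.1 compares potential severe hypoglycemia reported that way by Fisher's exact test, and Protocol section 10.3.4 compares serious events by the same test. The proportions are reported directly, and patients with severe events are listed. This largely stands. It is not a full substitute, because the section 6.12.4.1 comparison rests on a term search and does not state the three windows.

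A reader might infer that the SAP prescribes a Wald test and so would report no difference in a case such as 0 vs 6. The documents do not support that. The cell names no test, and the likelihood-ratio test of the same model rejects at 0 vs 6 (p = 0.004). The Fisher comparison elsewhere also means that one cell's p-value is not the plan's only answer.

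It can also be said that the endpoint is minor. The listed objective is the severe event rate, compared by a separate empirical method, and SAP section 6.5 applies no multiplicity adjustment outside the primary and multiplicity-adjusted objectives. That is correct and limits the impact. Finally, the postmeal rows concern a sparser endpoint, so Fisher's test there does not contradict a logistic model here; it only shows that the plan already accepts the exact test for data of this kind.

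**Conclusion.** The concern holds in a limited form. The method written in this cell gives no finite odds ratio or Wald interval when one arm has no events, and no estimate when neither has any. It also leaves the p-value undefined among tests that disagree: 0.018 to 0.999 for 0 vs 4, and 0.004 to 0.999 for 0 vs 6.

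How often this arises rests on an assumed incidence, equal in both arms, with 175 patients per arm. Exactly one empty arm over 26 weeks has probability 49% at 0.5%, 29% at 1%, 6% at 2% and 1% at 3%. Above about 3% the problem nearly disappears in the 26-week window.

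The defect is an unusable estimate and an unspecified test, not a routinely missed safety signal. A change in significance between Wald and Fisher has under 1% probability at equal risks of 0.5% to 2%, and about 6% to 18% under the assumed imbalances. The primary and other alpha-controlled conclusions are unaffected. The change is worth making because it is simple and removes a choice that would otherwise be made after seeing the data.

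**What to change.** In the Table 6.5 row for incidence of severe events, replace the logistic model with one of the following, for all three windows:

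- Fisher's exact test with an exact or score confidence interval for the difference in proportions. This matches the postmeal severe incidence row and the section 6.1 default.
- Firth-penalized logistic regression with a penalized-likelihood confidence interval and test, if an odds ratio is wanted.

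Add that when neither arm has an event, only the proportions are reported. Choose one option before unblinding, because the two can differ (0 vs 5: Fisher 0.061, Firth 0.026). The cost is one edited SAP cell, with no new data and no change to sample size or conduct. Since Protocol section 10.3.4 names logistic regression for incidence, record the change and its reason in the SAP; the plan's own rule requires an amendment only for a principal feature.

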#### 6.12.4.2. Systemic Hypersensitivity Reaction

The number and proportion of patients experiencing treatment-emergent potential systemic hypersensitivity reactions will be summarized and compared by treatment group using Fisher's exact test. The following Standardised MedDRA Query (SMQ) will be used to identify potential systemic hypersensitivity reactions from all TEAEs:

- Anaphylactic reaction (SMQ). Besides using the narrow and broad terms designated within the SMQ, the following search algorithm will also be implemented as another approach to determine if a patient had an anaphylactic reaction: if a patient (had at least 1 event in Category A) or (had at least 1 event that is in category B and also had at least 1 event that is in category C) or (had at least 1 event that is in category D and [also had at least 1 event in category B or at least 1 event in category C]).
- Angioedema (SMQ)
- Hypersensitivity (SMQ)

Specifically, need to perform the following: (1) any narrow or algorithmic term from any 1 of the 3 SMQs indicated above (that is, combined search across narrow and algorithmic portions of all 3 SMQs); (2) any narrow scope term within each SMQ, separately (that is, narrow SMQ search); (3) any term within each SMQ, separately (that is, broad SMQ search); (4) narrow scope term search within each SMQ, report the PT nested within each SMQ.

A similar summary will be provided using the TEAEs reported by the investigator as possibly related to study drug.

Note that an individual patient may contribute multiple events. Also, a single event may satisfy multiple SMQs, in which case the event contributes to every applicable SMQ.

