The number and percentage of patients who experienced an SAE, including deaths and SAEs temporally associated or preceding deaths, will be summarized by treatment group using MedDRA PT (without regard to SOC). Events will be ordered by decreasing frequency. A listing of all SAEs will also be provided.

The number and percentage of patients who discontinued from study due to an AE will be summarized by treatment group using MedDRA (without regard to SOC) using all data regardless of IP use. The number and percentage of patients who discontinued IP due to an AE will be also summarized by treatment group using MedDRA PT (without regard to SOC) using data prior to discontinuation of IP. Events will be ordered by decreasing frequency. A listing of all AEs as reason for study or IP discontinuation will also be provided.

The number and percentage of patients who experienced other notable TEAEs (potential systemic hypersensitivity reaction, injection site reaction, and hepatic disorder) will be summarized by treatment group using all TEAEs regardless of IP use.

For events that are gender-specific (as defined by MedDRA), the denominator and computation of the percentage will include only patients from the given gender.

Table 6.4 summarizes the planned analyses and the requirement of analysis data for different analysis periods. A 'Yes' in the IP USE column indicates that only data collected prior to discontinuation of IP will be included.

Analysis Period	Analysis Population	Analysis	IP USE	Treatment
Lead-in Period	All enrolled patients	AE overview; TEAE by PT, SAE, discontinuation from study due to AE	N/A	Open-label insulin lispro
Treatment Period (0-26 Weeks)	All patients in safety population	AE overview; TEAE by SOC and by PT; common TEAE; TEAEs by maximum severity; SAE; discontinuation from IP due to AE	Yes	LY900014, insulin lispro,
Week 0 – Visit 801	All patients in safety population	AE overview; TEAE by SOC; common TEAE; SAE; other notable AEs; study discontinuation due to AE	All data regardless of IP use	LY900014, insulin lispro

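### The algorithmic anaphylaxis search in SAP 6.12.4.2 has no time condition, so unrelated events months apart can flag a patient as a potential anaphylactic reaction (minor)

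*SAP*

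**What the plan says.** SAP 6.12.4.2 uses three SMQs (anaphylactic reaction, angioedema, hypersensitivity) "to identify potential systemic hypersensitivity reactions from all TEAEs". For the anaphylactic reaction SMQ, an algorithm "will also be implemented as another approach to determine if a patient had an anaphylactic reaction", alongside the narrow and broad terms. A patient is matched in one of three ways:

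- any category A event;
- the patient "had at least 1 event that is in category B and also had at least 1 event that is in category C";
- a category D event together with a B or a C event.

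The conditions apply to the patient. None refers to a common date, an episode or an interval.

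SAP 6.12.2 says that the notable TEAEs, including this group, "will be summarized by treatment group using all TEAEs regardless of IP use". Table 6.4 puts them in the Week 0 to Visit 801 period, and Table 6.2 gives the matching TEAE window as first dose of randomized IP to Visit 801.

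Section 6.12.4.2 lists four outputs. The first is the "combined search across narrow and algorithmic portions of all 3 SMQs". The other three are narrow terms by SMQ, any term by SMQ, and narrow preferred terms nested within each SMQ. The potential reactions "will be summarized and compared by treatment group using Fisher's exact test". The section also states: "A similar summary will be provided using the TEAEs reported by the investigator as possibly related to study drug".

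**The concern.** An anaphylactic reaction is a single acute episode. Pairing findings from different categories makes sense as evidence of one only if they occur together. As written, a category B event in Week 2 and an unrelated category C event in Week 25 meet the rule.

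The planned outputs would not reveal this. Algorithmic hits are merged with the narrow terms of all three SMQs, and the section plans no listing of the pairs with onset dates. Narratives under SAP 6.12.8 cover deaths, SAEs, discontinuations due to AEs and pregnancies, so a patient with two non-serious events who stays on treatment gets none. A reader of the combined row could not tell a chance pair from a real reaction. Where true cases are few, one or two chance pairs in an arm would be a visible part of the algorithmic contribution.

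The SAP does consider timing elsewhere. Section 6.12.4.1 merges hypoglycemia events no more than 30 minutes apart, and section 6.12.4.4.3 reviews how close transaminase and bilirubin elevations are to each other.

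**Working it through.** The plan gives no figure for this search, so there is none to reproduce. The check covers the length of the window, the size of the chance count and the effect of a time condition.

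**Window.** Protocol 5.1: 26 weeks of treatment + 4 weeks of safety follow-up = 30 weeks = 210 days.

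**Arm size.** Protocol 10.1: about 350 randomized 1:1, so 350 / 2 = 175 per arm.

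**Category incidences.** Not in the documents. Assumed 30-week incidences per patient: B 5-10%, C 3-6%, D 1-3%, independent of each other.

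**Chance matches without a time condition.** A patient matches by pairing if at least two of B, C and D occur:

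P = BC + BD + CD − 2·BCD

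- Low end (5%, 3%, 1%): 0.0015 + 0.0005 + 0.0003 − 0.00003 = 0.00227. Times 175 = 0.40 patients per arm.
- High end (10%, 6%, 3%): 0.0060 + 0.0030 + 0.0018 − 0.00036 = 0.01044. Times 175 = 1.8 patients per arm.

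For the row actually reported this is a ceiling under these assumptions, because a patient who already has a narrow term in any of the three SMQs is counted there anyway. One assumption works the other way: if patients who report one event tend to report others, independence understates the pairs.

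**Effect of a time condition.** For two independent onset days spread evenly over 210 days:

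- same day: 1 / 210 = 0.48%;
- same or adjacent day: (210 + 2 × 209) / 210² = 628 / 44,100 = 1.42%.

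A simulation of B/C pairs (2,000,000 patients per scenario, constant rates, repeat events allowed) agrees. About 0.3-0.6% of chance matches fell on the same day and about 1.5-1.9% within one day. Expected chance matches among all 350 patients:

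| Assumed B / C | No window | Within 1 day | Same day |
|---|---|---|---|
| 2% / 2% | 0.14 | 0.003 | 0.0005 |
| 5% / 5% | 0.88 | 0.013 | 0.003 |
| 10% / 10% | 3.5 | 0.05 | 0.02 |
| 15% / 15% | 7.9 | 0.14 | 0.04 |

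A one-day condition therefore removes over 98% of chance matches, whatever the incidences.

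**Effect on the comparison.** If chance gave 2 of 175 in one arm and 0 of 175 in the other, the two-sided Fisher p is 2 × (175 × 174) / (350 × 349) = 0.50.

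**The case against.** The strongest reply is that this is a screen and is labelled as one. The section speaks of potential reactions, and the algorithm supplements the term searches. It feeds only the combined row. The narrow and broad rows for the anaphylactic reaction SMQ use no pairing, and the broad row is looser still because a single term suffices. A further summary is limited to TEAEs judged possibly related. Serious reactions appear in the SAE listing and have narratives. The category terms are not listed and no incidences are given, so neither the number of chance pairs nor how minor the paired events are can be established. A tight window could also cost sensitivity.

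Much of this stands, and it rules out two stronger readings:

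- A reader might infer that the trial's anaphylaxis count will be inflated. The documents do not support that: no listed output is an algorithmic anaphylaxis count, and the anaphylaxis-specific rows do not use the algorithm.
- A reader might infer a bias against LY900014. The rule is the same in both arms. Chance pairs grow roughly with the product of the B, C and D incidences, so an arm with more of those particular events would gain more of them. Nothing in the documents predicts such an imbalance; Protocol 3.3 reports no clinically significant increase in the AEs associated with systemic treprostinil.

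What the reply does not supply is a time condition. Calling a case potential does not explain why events five months apart should form one candidate reaction. The possibly-related summary narrows the events but adds no window. The sensitivity cost is met by keeping untimed pairs in a listing.

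**Conclusion.** The point holds as a minor one. Followed literally, the rule flags events up to about 30 weeks apart as one potential anaphylactic reaction, and no other section adds a window or a case review for these matches. The effect is confined to the combined narrow-or-algorithmic row and its counterpart, if produced, in the possibly-related summary. Its size is unknown from the documents. Under the assumed incidences and independence it is at most about 0.4 to 1.8 patients per arm of 175. With similar event rates in the arms this is mainly noise in one Fisher comparison. The primary and multiplicity-adjusted analyses are not touched.

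**What to change.** Add to SAP 6.12.4.2 that the paired events (B with C, D with B, D with C) must start within a prespecified short interval, for example on the same or the next calendar day. Use the timed result in the combined row, and apply the same rule in the possibly-related summary. List all untimed pairs with their onset dates for medical review.

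The cost is one sentence, a date condition in the program and one listing; no data collection changes. The exact interval is a choice for the sponsor's safety physicians, made before unblinding. The small downside is that a true pair with a misrecorded onset date appears only in the listing and not in the table.
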